##### *7.7.2. Analysis supporting secondary objectives*

Generalized mixed linear models will be used as previously described to compare arm 1 and arm 2 vs arm 3, sitting the following parameters expressed in terms of change from baseline to the end of the study (month 6): inflammatory biomarkers (CRP, etc), IGF-1, blood pressure, serum lipids, glucose, CV biomarkers and, body weight, BMI, body composition, insulin resistance, aging biomarkers, sleep quality and duration, and number of participants who receive antihypertensive/hypoglycaemic medications.

We will also evaluate the effect of FMD and FMD+LD treatments on risk factors for CVD and metabolic syndrome, defined as three of five of the following conditions: abdominal obesity, elevated fasting glucose, elevated blood pressure, high serum triglycerides, and low HDL cholesterol.

We will select clinically relevant cutoffs and compared normal and at-risk subjects for each risk factor: total cholesterol >199 mg/dl and LDL cholesterol levels >130 mg/dl are associated with an increased risk for CVD, a fasting glucose >99 mg/dl indicates impaired fasting glucose/prediabetes, and triglyceride levels >100 mg/dl as well as CRP >1 mg/liter are associated with increased risk for CVD. For serum IGF-1, no clinically relevant risk level has been established, but a number of epidemiological studies have associated IGF-1 levels above 200 ng/ml with various cancers (Levine et al., 2014; Pollack et al., 2007). We will therefore compare the effect of FMD/FMD + LD cycles on subjects in the highest quartile of IGF-1 expression (>225 ng/ml) with that on subjects with IGF-1 levels ≤225 ng/ml. The effect of FMD and FMD+LD treatments on these risk factors will be assessed also stratifying our sample by baseline BMI, SBP and DBP, fasting glucose, cholesterol, CRP and IGF-

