#### *7.4. Sample Size Consideration*

Sample size determination was based on the power to detect a significant effect of FMD nutritional intervention on fat mass during the treatment period (6 months) with respect to the control group. The primary hypothesis of this trial can be formally stated as a test of whether there is a time × intervention interaction. In particular, assuming a low effect size of the FMD intervention (Cohen's  $F = 0.10$ ) and a correlation coefficient among the repeated measures equals to 0.5, a sample size of 107 participants per group, would give a power of at least 0.9 for testing the hypothesis of whether there is a time × intervention interaction at a significance level of 0.05. With an estimated dropout rate of 30%, at least 153 participants would need to be recruited in each arm. For this reason, we will enrol 501 participants that will be randomly assigned to each of the three arms (167 for each arm).

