#### *7.7. Study conclusions*

Collected data from subjects will be reviewed to demonstrate that favorable changes are noted in biomarkers of body composition and age-related biomarkers with administration of the proprietary food products. Data will be evaluated for change from baseline over time within arms and for differences between the intervention arm and the control arm.

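### The at-risk versus normal comparisons in 7.7.2 do not require a contrast with the control arm, so read literally they would show regression to the mean as diet benefit

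*Protocol*

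**What the plan says.** Section 7.7.2 opens with mixed models that compare arms 1 and 2 with arm 3 on change from baseline to month 6. Further on it adds other comparisons:

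- **Risk factors.** "We will select clinically relevant cutoffs and compared normal and at-risk subjects for each risk factor". Fixed cutoffs follow for total cholesterol, LDL cholesterol, fasting glucose, triglycerides and CRP. The two sides are at-risk and normal subjects; no arm is named.
- **IGF-1.** The plan is to "compare the effect of FMD/FMD + LD cycles on subjects in the highest quartile of IGF-1 expression (>225 ng/ml") with the effect in subjects at or below that value. Arm 3 is not mentioned.
- **Stratification.** The treatments' effects on these risk factors are also to be examined by baseline values of several of the same markers.

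Section 7.7 states: "Data will be evaluated for change from baseline over time within arms". The same sentence goes on to include differences between intervention and control, so both kinds of evaluation are planned. The sentence before it gives the purpose of the review as demonstrating favourable changes.

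Section 7.7.4 on subgroups covers baseline fat mass, age, gender and BMI, and none of these blood markers.

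**The concern.** When subjects are grouped by the baseline value of a marker and then compared on change in that marker, those above the cutoff fall on average and those below it rise, whatever they eat, because repeat measurements are imperfectly correlated. A comparison of at-risk with normal subjects inside a diet arm therefore mixes any diet effect with regression to the mean. The control arm would remove that part, but the wording does not require its use here.

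Two features of the design bear on this. Section 3.3.3 allows blood results to be carried over from screening, so one measurement can both classify a subject and start the change score. The entry criteria in 3.1.1 also select on some of the same markers; CRP above 1 mg/L is both an entry criterion and an at-risk cutoff. That selection is diluted, because any one of seven criteria, including obesity, is enough.

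At stake is how any larger fall in at-risk subjects would be read, since an inert diet would produce the same pattern.

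**Working it through.** **Inputs from section 7.4.** Cohen's f = 0.10 ("assuming a low effect size of the FMD intervention"); "a correlation coefficient among the repeated measures equals to 0.5"; test "at a significance level of 0.05"; "a sample size of 107 participants per group, would give a power of at least 0.9"; "With an estimated dropout rate of 30%, at least 153 participants would need to be recruited in each arm".

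**The plan's own figure.** For a within-between interaction with k groups, m measurements and N subjects in total, the noncentrality is λ = f²·N·m/(1 − ρ), with (k − 1)(m − 1) and (N − k)(m − 1) degrees of freedom.

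- k = 3, m = 2, N = 321: λ = 0.01 × 321 × 2/0.5 = 12.84; df 2 and 318; power 0.902.
- k = 2, m = 3, N = 214: λ = 0.01 × 214 × 3/0.5 = 12.84; df 2 and 424; power 0.902.
- Dropout: 107/0.7 = 152.9, so 153.

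The figure reproduces and is not in dispute. It matters here only as the source of ρ = 0.5 and of a plausible number of completers.

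**Assumptions for the artefact.** Baseline and follow-up are bivariate normal with equal variances and correlation ρ, and the diet has no effect. The same baseline value classifies the subject and starts the change score. The cut is at the top quartile, as the IGF-1 sentence describes; the share above the other cutoffs is not given. The value 0.5 is stated for fat mass and none is given for blood markers, so a range of 0.5 to 0.9 is shown.

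**Expected change.** In SD units, E[change | baseline z] = −(1 − ρ)·z. The mean z is 1.271 in the top quartile and −0.424 in the rest, a gap of 1.695. The expected difference in change, top quartile minus the rest, is therefore −1.695·(1 − ρ).

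| ρ | Top quartile | Rest | Difference |
|---|---|---|---|
| 0.5 | −0.64 | +0.21 | −0.85 |
| 0.7 | −0.38 | +0.13 | −0.51 |
| 0.8 | −0.25 | +0.08 | −0.34 |
| 0.9 | −0.13 | +0.04 | −0.17 |

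A cut at the median gives nearly the same differences: −0.80 at ρ = 0.5 and −0.16 at ρ = 0.9.

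**How often it would be significant.** Simulated share of trials in which a two-sided 5% t-test of top quartile against the rest, within one arm and with no diet effect, rejects. The sizes are 107 (the evaluable number in 7.4), 117 (167 × 0.7 = 116.9) and 167 (no dropout).

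| ρ | n = 107 | n = 117 | n = 167 |
|---|---|---|---|
| 0.5 | 98% | 99% | 99.9% |
| 0.7 | 85% | 88% | 96% |
| 0.8 | 69% | 72% | 86% |
| 0.9 | 40% | 42% | 57% |

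**With the control arm.** Under randomisation each baseline category regresses equally in both arms in expectation. In the same simulations (117 and 167 per arm), subtracting the control arm's contrast brings the mean difference to about 0.00 SD. The false-positive rate is 4.7% to 5.9% across settings, both for diet versus control within the top group and for the arm by category interaction.

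**The case against.** The best defence is that the control arm is already implied. Section 7.7.2 opens with arms 1 and 2 against arm 3, and the IGF-1 and stratification sentences speak of the effect of the diets, which in that setting can well mean effect versus control. Section 7.7 names the control comparison in the same sentence as within-arm change. On that reading regression to the mean cancels. This stands for the IGF-1 sentence, where the uncontrolled reading is only one of two. It is weaker for the at-risk versus normal sentence, which mentions neither an effect nor an arm.

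A reader might infer that the trial will show a benefit in at-risk subjects through regression to the mean alone, or that the protocol plans to conclude that the diet helps those subjects most. The documents support neither. The first holds only if the analyst leaves the control arm aside, which the text permits but does not direct. The second is stated nowhere.

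The rates near 99% also need care: they use a correlation stated for fat mass and a top-quartile split that the protocol links only to IGF-1.

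Finally, these are secondary analyses in a study that 7.1 calls exploratory, and such detail is often left to a separate SAP. But 7.7.2 does fix the cutoffs and the two sides of the comparison, so a SAP that followed it literally would carry the problem forward.

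**Conclusion.** The concern holds as an unspecified contrast. The at-risk versus normal sentence, and less clearly the IGF-1 comparison, do not require a contrast with control, and 7.7 leaves room for within-arm change to be used as evidence. Analysed literally, an inert diet would give an apparent advantage to the at-risk group of 0.85 SD at a correlation of 0.5, falling to 0.17 SD at 0.9, with false positives in roughly 99% to 40% of trials at 107 to 117 completers per arm. These sizes rest on normality, equal variances, a top-quartile cut and an assumed correlation range for the blood markers. If a separate screening draw classified subjects and a fresh baseline draw started the change score, the artefact would be smaller. If effect means effect versus control, it is zero on average. The protocol's primary comparison with control is not affected.

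**What to change.** In 7.7.2, state that the effect in each baseline category is the difference in change between FMD (or FMD+LD) and control within that category. State also that differences between categories are tested by the arm by baseline-category interaction in the mixed model, or by the interaction of arm with continuous baseline. In 7.7, state that within-arm changes are descriptive and do not support conclusions on efficacy.

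The change needs no new data, visits or participants. The cost is precision: with equal arms and equal variances, the difference between two independent contrasts has a standard error √2 ≈ 1.41 times that of the single-arm contrast. That loss is the price of removing the bias.

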### 3.1. Selection and withdrawal of subjects

#### 3.1.1. Inclusion Criteria

- Subjects of 30-65 years of age;
- Body mass index equal to or greater than 25 kg/m^2.  
And at least one of the following:
- obesity (Body mass index equal to or greater than 30 kg/m^2).
- HbA1C greater than 5.6% (38 mmol/mol);
- IGF-1 level greater than 200 ngml;
- systolic blood pressure >130 mmHg and diastolic blood pressure >90 mmHg; the inclusion of individuals currently taking antihypertensive medications is allowed. In this last case a careful attention will have to be paid to the self-monitoring of blood pressure during the FMD cycles;
- triglycerides >150 mgdl;
- C-reactive protein >1 mgL;

- total cholesterol >190 mgdL and LDL cholesterol >129 mgdL.

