#### *7.7.4.Subgroup analyses*

To explore the effect of treatment in subgroups, the estimated effect of the nutritional interventions will be estimated for each of the subgroups listed below will be derived. No adjustment for multiple comparisons will be made. Additionally, the frequency and percentage of subjects reaching the primary endpoint will be presented by treatment group for each of the subgroups based on the baseline measurements: baseline fat mass ( $\geq 20\%$  and  $\geq 25\%$  for men;  $\geq 30\%$  and  $\geq 35\%$  for women), age groups (30-50, 51-65 years), gender, baseline BMI (25-29.9; 30 and over);

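### Section 7.7.2 judges whether baseline IGF-1 modifies the diet effect by a single cut at 225 ng/ml that the protocol does not justify, and it describes no analysis with IGF-1 as a continuous modifier

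*Protocol*

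**What the plan says.** Section 7.7.2 (secondary objectives) sets the general approach to the risk factors: "We will select clinically relevant cutoffs and compared normal and at-risk subjects for each risk factor". For total and LDL cholesterol, glucose, triglycerides and CRP it names a cut-off and gives a clinical reason, either cardiovascular risk or impaired fasting glucose.

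IGF-1 is handled differently. The section states: "For serum IGF-1, no clinically relevant risk level has been established". It then offers an epidemiological reason: "a number of epidemiological studies have associated IGF-1 levels above 200 ng/ml with various cancers". From this it concludes that the effect of the diet cycles will be compared between "subjects in the highest quartile of IGF-1 expression (>225 ng/ml) with that on subjects with IGF-1 levels ≤225 ng/ml".

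The value 200 also appears in section 3.1.1, where "IGF-1 level greater than 200 ngml" is one of several alternative entry criteria. The value 225 appears nowhere except in the comparison itself.

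A final sentence says that the effects "will be assessed also stratifying our sample by baseline BMI, SBP and DBP, fasting glucose, cholesterol, CRP and IGF", where the text breaks off. It gives no cut points or number of strata. No interaction test is named, and no baseline marker is described as a continuous modifier.

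**The concern.** Comparing the diet effect at high and low baseline IGF-1 is a question about effect modification by a continuous measurement. A single cut treats 226 and 400 ng/ml as the same, 224 and 80 as the same, and 224 and 226 as different. If the diet effect changes gradually with baseline IGF-1, much of the evidence for that is discarded. The loss comes from the cut, so it remains even if the two groups are properly compared with control through an interaction test.

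For IGF-1 the boundary also lacks support within the document. The paragraph disclaims an established risk level, cites 200, and then uses 225 without linking the two. It calls the group above 225 the highest quartile, but a value fixed before enrolment and a quartile of the enrolled sample agree only by chance.

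At stake is a missed graded relation, or a result that depends on where the line was drawn. With 200, 225 and the observed quartile all available, the boundary could also be reconsidered after the data are seen, in an open-label trial.

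**Working it through.** **The plan's own figures.** The protocol states no power for this comparison. The nearest figures are in section 7.4: Cohen's f = 0.10, correlation 0.5, alpha 0.05, 107 per group for power of at least 0.9, and 30% dropout. For the time-by-group F test, λ = f²·N·m/(1−ρ), with N participants in all and m visits. At 107 per group this gives power 0.902 both for 2 groups × 3 visits and for 3 groups × 2 visits, so 107 is reproduced. Dropout: 107/0.7 = 152.9, hence 153 as stated. With 167 enrolled per arm, completers are 167 × 0.7 = 116.9, about 117.

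**Information kept by the cut.** Assume a normal marker, a linear modification, and a share p of participants above the cut. The information kept, relative to the continuous marker, is φ(z)²/[p(1−p)], where z is the cut on the standard normal scale.

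- p = 0.25: z = 0.674, φ = 0.3178; 0.3178²/0.1875 = 0.539. Loss 46%; 1/0.539 = 1.86 times the participants would be needed to recover it.
- p = 0.50: 0.3989²/0.25 = 0.637. Loss 36%.
- p = 0.10: z = 1.282, φ = 0.1755; 0.1755²/0.09 = 0.342. Loss 66%.

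The protocol's term highest quartile gives p = 0.25. The range 0.10 to 0.50 is my assumption, because the share above 225 in this trial is not known.

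**Other marker shapes, cut at the top quartile.** Loss is 44% for a uniform marker, about 39% for mildly to moderately log-normal markers (log SD 0.3 and 0.5), and 56% for a strongly log-normal one (log SD 1).

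**Power, one diet arm against control, 117 per arm.** The slopes are assumptions, in outcome SD per marker SD; the document gives none. A slope of (1.96 + 0.8416) × √(2/117) = 0.366 has 80% power on the continuous scale. With the top-quartile cut the power is Φ(2.8016 × √0.539 − 1.96) = 54%. Simulation gives 79% continuous against 52% cut. At a slope of 0.30 it gives about 60% against 38%, and at 0.20 about 35% against 21%.

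**When the truth is a step.** For a step of the same overall size exactly at the cut, the order reverses: about 52% continuous against 79% cut. For a step elsewhere (top 40% of the marker), the continuous test is again somewhat better, about 57% against 49%.

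**The case against.** The strongest objection is that the functional form of an exploratory modifier model is normally left to the SAP, which is not shown. That would answer a complaint about silence. Here, however, the protocol states the method for IGF-1: two groups, a named boundary, and a comparison of effects between them. An SAP could add a continuous analysis, so the fair statement is that the protocol describes none.

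A second objection is that the section asks about normal and at-risk subjects, which is a threshold question, and that the cut is the better test if the effect really steps at the boundary. This stands as a limit: no dose-response hypothesis is written down, and neither method is better for every shape. For IGF-1, though, the protocol itself disclaims an established risk level and gives no reason to expect a step at 225.

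A third is that the slopes are generous. This also stands. If both diets act equally (3 groups × 2 visits), f = 0.10 with correlation 0.5 corresponds to a difference in change of 0.10 × √18 = 0.42 SD. A modification of 0.37 SD per marker SD is nearly as large as that treatment effect, and at 0.20 neither analysis has adequate power.

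A reader might also infer more than the text supports:

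- That the 46% applies to every marker. It does not: only the IGF-1 group is called a quartile, the shares above the other cut-offs are not given, and those cut-offs have stated clinical reasons.
- That every marker is tested only in two groups. The closing stratification sentence gives no strata and breaks off, and no test is named.
- That IGF-1 levels in this region are said to have no meaning. The protocol says only that no clinical risk level is established, and it does give an epidemiological reason, at 200.

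**Conclusion.** The point holds for IGF-1. Section 7.7.2 commits to a comparison across 225 ng/ml, a value its own reasoning does not reach, and the protocol describes no continuous analysis beside it. For a linear modification and a roughly normal marker, the cut loses about 46% of the information if 25% of participants exceed 225, and about 36% to 66% for shares from 50% down to 10%. The loss rests on the modification being graded; a true step at 225 would favour the cut.

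The consequence is small. Section 7.1 calls the study exploratory, these are supporting secondary comparisons, and the primary analysis in 7.7.1 and the sample size in 7.4 are untouched. It is a cheap improvement and does not threaten the trial's main conclusion.

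**What to change.** In section 7.7.2, define the effect-modification analysis for IGF-1 as a baseline-marker-by-arm term, each diet against control, with IGF-1 continuous: on the log scale if skewed, with a spline if the relation may be non-linear. Show the estimated diet effect with its confidence interval across the IGF-1 range. Do the same for the other baseline markers as a supplement. Keep the >225/≤225 ng/ml table and the normal/at-risk tables as descriptive summaries.

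The cost is analysis wording and some extra model output; no data, visits or participants are added. The downside is lower power if the effect truly steps at exactly the chosen cut-off, and the retained tables would still display such a step.

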#### *7.7.3.Safety and Tolerability/Acceptability Evaluation*

Collected data from subjects will be reviewed for occurrence of AEs and for data concerning hedonics, tolerability and acceptability of products. CMP and CBC data will be tallied and evaluated. This information will be considered in drafting any product instructions and warnings.

#### *7.7.4.Subgroup analyses*

To explore the effect of treatment in subgroups, the estimated effect of the nutritional interventions will be estimated for each of the subgroups listed below will be derived. No adjustment for multiple comparisons will be made. Additionally, the frequency and percentage of subjects reaching the primary endpoint will be presented by treatment group for each of the subgroups based on the baseline measurements: baseline fat mass ( $\geq 20\%$  and  $\geq 25\%$  for men;  $\geq 30\%$  and  $\geq 35\%$  for women), age groups (30-50, 51-65 years), gender, baseline BMI (25-29.9; 30 and over);

### **8. Ethical Considerations**

#### *8.1. Declaration of Helsinki*

The investigator will ensure that this study is conducted in full conformity with the current revision of the Declaration of Helsinki, or with the International Conference for Harmonization Good Clinical Practice regulations and guidelines, whichever affords the greater protection to the subject.

#### *8.2. Informed Consent Process*

Informed consent is a process that is initiated prior to the individual agreeing to screen for and participate in the study and continuing throughout the individual's study participation. Extensive discussion of risks and possible benefits of this therapy will be provided to the subjects. Consent forms describing in detail the Study Product, the study procedures and associated risks will be given to the Subject and written documentation of informed consent is required prior to screening for the study and if qualified, prior to starting the study. The subject will be asked to read and review the document. Upon reviewing the document, the investigator or designee will explain the research study to the Subject and answer any questions that may arise. The subjects will sign the informed consent document prior to any procedures being done specifically for the screening process and if qualified, for the study. The subjects will have sufficient opportunity to discuss the study and process the information in the consent process prior to agreeing to participate. The subjects may withdraw consent at any time throughout the course of the trial. A copy of all informed consent documents will be given to the subjects for their records.

The acquisition of informed consent will be documented in the subject's medical records. The informed consent form will be signed and personally dated by the subject and the person who conducted the informed consent discussion. The original signed informed consent form will be retained in the medical chart and a copy will be provided to the subject.

The study poses minimal risk for the participants. The anonymized information collected in the study will be used for research and publication purposes, and always safeguarding the right of privacy and anonymity according to the rules of General Data Protection Regulation (GDPR) of the European Union (UE) 2016/679.

This study will be initiated only after all required legal documentation has been reviewed and approved by the University of Calabria Ethic Committee, according to the national and international regulations. The same applies for the implementations of changes introduced by amendments.

Individual patient medical information obtained as a result of this study is considered confidential and disclosure to third parties is prohibited with the exception noted below. Patient confidentiality will be ensured by using patient identification code number.

The biological samples will be stored for 15 years under liquid nitrogen at the Laboratory of Genetics of the University of Calabria and thereafter destroyed. They will undergo a coding process with measures taken to ensure that specimens are kept under correct conditions always when it is stored. Each sample will be assigned to an identification code, which will be used by researchers and will prevent third parties from identifying the study participants from their samples. Encryption and access passwords will be adopted to protect and safeguard the stored samples.

